## 7.6 Dosing Delays and Subject Replacement

In case there is an interruption of treatment or if any medication dose is missed this would be captured and subsequently documented on the Dosage Administration Case Report Form (CRF). If the patient's treatment is interrupted, the missed dose will not be replaced. If a patient misses a study dose due to noncompliance (as determined by the treating physician), then the patient would be removed from the study. Subsequently this subject would need to be replaced. If the treatment is interrupted for 1 week due to adverse effect(s) from study medication therapy, then the patient would be removed from the study and the subject(s) would not be replaced.

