## **4.0 STUDY DESIGN**

### **4.1 Overall Design**

This is a single institution, single arm, non-randomized phase II clinical trial with a sample size of 31 patients. The primary goal of this trial is to determine if eltrombopag can accelerate platelet count recovery in older AML patients (age  $\geq$ 60 years) who have no morphological evidence of leukemia in the bone marrow following remission IC. The standard remission IC for AML in patients  $\geq$ 60 years will consist of an anthracycline (daunorubicin or idarubicin) for 3 days and cytarabine as continuous intravenous infusion for 7 days. The patients in the study will receive supportive blood transfusions as part of standard of care at the Cleveland Clinic. Use of erythropoiesis stimulating agents (ESA) or granulocyte colony stimulating factors (G-CSF) during or following remission IC is not permitted. The study schema is shown below.

In those patients who have no morphologic evidence of disease on day 14 (range, 14-17) bone marrow evaluation, eltrombopag will be administered within 5 business days from the date of day 14 (range, 14-17) bone marrow biopsy. There will be a gap of at least one week (range, 7-9 days) between the last day of remission IC and initiation of eltrombopag, which will allow sufficient time for complete washout of the chemotherapeutic agents. Dose modification will be determined based on platelet counts and presence of adverse event(s).

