### 7.3 Dose Adjustments for Eltrombopag

If after 2 weeks, the platelet count fails to reach 50,000/ $\mu$  L or above, the dose will be increased to 300 mg orally daily (150 mg orally daily for East-Asians). Depending on tolerability, dose modification will be individualized based on the patient's platelet count response according to the following rules:

Dose Modification / Adjustment of Eltrombopag	
If platelet count is $\leq$ 50,000/ $\mu$ L after 2 weeks of treatment with starting dose of eltrombopag*	Increase daily dose to 150 mg for East-Asians and 300 mg for all other ethnicities
If platelet counts are between 50,000 and $<$ 100,000/ $\mu$ L (untransfused) on the starting or escalated dose of eltrombopag	Continue on the same dose
If platelet counts reach $\geq$ 100,000/ $\mu$ L (untransfused) on the starting or escalated dose of eltrombopag at any time on study	Discontinue eltrombopag

\* Starting dose will be 100 mg for East-Asians and 200 mg for other ethnicities.

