## 7.7 Duration of Therapy and Off Study Criteria

Depending on tolerability, eltrombopag can be administered to all assigned study subjects for a total duration of 4 weeks (counted from the first day of eltrombopag administration) unless they meet one of the following criteria for removal from the study:

1. Withdrawal of consent. The patient's desire to withdraw from the study may occur at any time. The investigator should carefully consider whether the patient's withdrawal of consent is due to an adverse event, and if so, record the adverse event as the reason for withdrawal.
2. Violation of the study protocol, including a patient's failure to return for required treatments or assessments or failure on the part of participants with reproductive potential to practice effective birth control or non-compliance.
3. At the treating physician's clinical discretion, if any specific medical or psychosocial changes in patient's condition makes them unacceptable to further participate in the study.
4. If bone marrow biopsy performed to establish remission status (around day 30-45 of remission IC), confirm refractory or persistent disease or if there is leukemic involvement of extramedullary site (biopsy confirmation of skin or organ lesions, central nervous system involvement confirmed either by cerebrospinal fluid analysis or radiological exams) at any time during study.
5. Adverse events, including intolerance of eltrombopag not resolved by dose reduction, life threatening acute hypersensitivity reaction, persistent hepatotoxicity (refer to section 7.4.2), thrombosis/embolism (DVT, PE, stroke, TIA, myocardial infarction) other than central line thrombosis (refer to section 7.5.1) or evidence of disease progression on treatment (myeloid sarcomas). Participants who are removed from the study due to adverse events will be treated and followed according to established medical practice. All pertinent information concerning the outcome of such treatment will be entered in the CRF.

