## 12.0 STATISTICAL CONSIDERATIONS

The primary goals of this trial are to assess the efficacy and safety of a short course of eltrombopag in elderly AML patients who have no morphological evidence of residual disease on bone marrow biopsy following standard 7+3 induction therapy. The primary endpoint is the proportion of patients with early (by day 24 from the start of induction) platelet recovery to  $\geq 50,000/\mu\text{L}$ . Based on historical data and our own institutional data (unpublished) approximately 60% of patients can be expected to recover platelets to  $\geq 50,000/\mu\text{L}$  by day 24 without additional supportive care beyond platelet transfusions. An increase in the recovery rate to  $\geq 80\%$  would be considered indicative that eltrombopag has significant efficacy in this population.

A two-stage accrual design with a maximum accrual goal of 31 eligible and evaluable patients will be used to test this hypothesis. Twelve eligible patients will be studied initially. If eight or more (67%) have full platelet recovery by day 24 an additional 19 eligible patients will be assessed. If overall 21 or more of the 31 patients have platelet recovery (observed recovery rate  $\geq 68\%$ ) eltrombopag will be accepted for further testing. With this design, there is a  $\geq 56\%$  likelihood of stopping early if eltrombopag's true recovery rate is  $\leq 60\%$ , whereas there is at most a 7% chance if the true recovery rate is  $\geq 80\%$ . The overall likelihood of rejecting eltrombopag if it is not active is  $\geq 81\%$  while there is at most a 9% chance of rejection if it is active.

Adverse events will be graded and categorized using CTCAE version 4.03 criteria. Assuming the trial reaches its maximum accrual goal of 31 eligible patients the likelihood of a particular type and/or grade of toxicity will be estimable using a 95% confidence interval that has a half-width of at most 18%. The likelihood of observing at least one such event is  $\geq 80\%$  even if the underlying risk is little as 5%.

Secondary goals of the trial include estimating the frequency of platelet transfusion independence, the effect of eltrombopag on hemoglobin, and neutrophils, the risk of clinically significant bleeding, clinical efficacy, and time to initiation of post-remission consolidation therapy.

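### Treated patients judged noncompliant are removed and replaced, even after day 24, and no all-treated set is named, so the primary denominator can depend on outcome

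*Combined protocol and SAP*

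**What the plan says.** Section 7.6 (Dosing Delays and Subject Replacement) sets two rules for treated patients.

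- If someone "misses a study dose due to noncompliance (as determined by the treating physician), then the patient would be removed from the study". It continues: "Subsequently this subject would need to be replaced". One missed dose is enough. There is no time limit and no exception for a patient whose day-24 result is already recorded.
- If dosing is interrupted for one week by an adverse effect of the drug, "then the patient would be removed from the study and the subject(s) would not be replaced".

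Section 12.0 (Statistical Considerations) describes "a maximum accrual goal of 31 eligible and evaluable patients". For the first stage it says "Twelve eligible patients will be studied initially", followed by 19 more eligible patients. The word evaluable appears once and is not defined. No all-treated set is named, and nothing says how removed or replaced patients count at 12 or at 31.

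On timing, Section 4.1 says that "eltrombopag will be administered within 5 business days from the date of day 14" (range 14-17) marrow, with a gap of 7 to 9 days after induction ends. Section 7.7 allows four weeks of dosing. Section 7.3 stops the drug once the untransfused count reaches 100,000/µL. Section 8.2 calls for daily blood counts in hospital.

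**The concern.** The primary endpoint is the proportion of patients recovering to 50,000/µL by day 24. Replacing a patient against a fixed total of 31 normally means that patient no longer counts. Three features let the outcome influence who is replaced.

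1. **Timing.** Most scheduled doses come after day 24, so a patient already known not to have recovered can still be removed and replaced.
2. **Unequal exposure to the rule.** A patient who reaches 100,000/µL stops the drug and cannot miss a later dose. A patient below 50,000/µL stays on it. This tilts removal towards non-recoverers without any bad faith.
3. **Knowledge.** The physician who judges noncompliance sees the platelet counts.

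If non-recoverers are removed more often, the observed recovery rate rises, and so does the chance of accepting an inactive drug. If removal is unrelated to recovery, nothing changes. If recoverers are removed more often, the bias reverses. The plan prespecifies nothing that would show which case applies.

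**Working it through.** **Inputs (Section 12.0).** Continue if at least 8 of 12 recover; accept if at least 21 of 31 recover; null rate 60%, target rate 80%.

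**The plan's own figures.** With recovery rate p:

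- P(stop early) = P(Bin(12, p) ≤ 7)
- P(accept) = Σ over x = 8 to 12 of P(Bin(12, p) = x) × P(Bin(19, p) ≥ 21 − x)

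| True rate | Stop early | Accept | Reject | Plan states |
|---|---|---|---|---|
| 60% | 56.2% | 19.4% | 80.6% | stop 56%, reject 81% |
| 80% | 7.3% | 91.1% | 8.9% | stop 7%, reject 9% |

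The plan's figures reproduce, provided the denominator does not depend on outcome.

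**Timing.** Seven days of induction plus a seven-day gap puts the first dose on day 14 at the earliest. Twenty-eight daily doses then run from day 14 to day 41: 11 by day 24 (days 14 to 24) and 28 − 11 = 17 after it. A later start leaves more after day 24.

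**Effect of replacement.** Let m be the share of treated patients replaced and q their recovery rate. At a true rate of 60%, 0.60 = m·q + (1 − m)·p_e, so the rate among those counted is

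p_e = (0.60 − m·q) / (1 − m).

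Example: m = 0.05 and q = 0 give 0.60 / 0.95 = 0.632. Putting p_e into the rule above gives the chance of acceptance:

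| Recovery rate of those replaced (assumed) | m = 2% | m = 5% | m = 10% |
|---|---|---|---|
| 0% (upper bound) | 23% | 30% | 44% |
| 30% | 21% | 24% | 31% |
| 43% (see below) | 20% | 22% | 25% |
| 60% (unrelated to recovery) | 19.4% | 19.4% | 19.4% |
| 80% | 18% | 16% | 14% |

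The 43% row assumes that missed doses are random among patients still on drug and that half of the recoverers have already stopped at 100,000/µL: q = 0.30 / (0.30 + 0.40) = 0.429. With a quarter or three quarters stopped, acceptance at m = 5% is 20% or 25%.

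**At the cut-off.** 21/31 is 68%. If one replaced non-recoverer is counted, it is 21/32 = 66% of those treated; with three, 21/34 = 62%.

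**The case against.** The strongest reply is that the key step is inferred. Neither section says a recorded day-24 result is discarded, and Section 12.0 mostly says eligible, a status that a later missed dose does not undo. That is fair. It shows the plan can be read two ways, and the reading that fits replacement against a fixed evaluable total is the harmful one.

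The direction is also uncertain. If slower recoverers stay in hospital longer, their doses are supervised, while recoverers between 50,000 and 100,000/µL may be taking the drug at home and missing more doses. The 80% row covers this, and the point stands.

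The size is open too. At 2% replacement, fewer than one patient in 31 is affected (0.02 × 31 = 0.6). The table assumes replacement can act before the 12-patient look. If stage-1 results stand once counted and only the 19 later patients are affected, acceptance with none recovering is 24% rather than 30% at m = 5%, and 29% rather than 44% at m = 10%. In the 43% scenario it is 20% to 22% across the three values of m. This narrows the effect but does not remove it.

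The plan has some protection: missed doses go on the case report form, and adverse-effect removals are not replaced. Removals could therefore be tabulated afterwards, although no such table is planned.

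Finally, day-24 counts might be missing after removal. Section 6.4 already has platelets monitored daily in hospital and weekly after discharge for four weeks after the drug stops. The outpatient interval is coarse, but the data collection exists.

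**Conclusion.** The concern holds. Followed as written, Section 7.6 together with the undefined evaluable total in Section 12.0 can make the primary denominator depend on outcome. The effect depends on two quantities that the documents do not give: how often patients are replaced for noncompliance, and how often those patients recover. At 5% replaced, false acceptance moves from 19.4% to between 16% and 30%. The scenario built on the plan's own stopping rule gives 22%, and 30% is an upper bound. The 44% figure needs 10% replaced with none recovering. The change should be made, because false acceptance already starts near one in five and, with 31 patients, the decision can turn on one of them.

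**What to change.** In Sections 7.6 and 12.0:

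- Define the primary set, for the 12-patient look and the final test, as all eligible patients who receive at least one dose.
- Score each on the actual platelet count by day 24 whatever the compliance, keep collecting that count after removal, and count an unobserved outcome as non-recovery.
- Limit replacement in the primary count to patients who never received a dose.
- Report the compliant-patient result as a sensitivity analysis, and list each removal with its reason, its date and whether it came before or after day 24.

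No dosing or removal rule needs to change; only the counting does.

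The cost is wording and some power. If every removed patient scored as a failure, the rate at the target becomes 0.80 × (1 − m), and power falls from 91% to 88%, 81% or 67% at 2%, 5% or 10% removal. If the day-24 count is obtained in half of those removed, the rate is 0.80 × (1 − m/2), and power is about 87% at 5% and 81% at 10%. Because most doses fall after day 24, many removals should already have a result, and the loss should then be smaller.

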## 7.7 Duration of Therapy and Off Study Criteria

Depending on tolerability, eltrombopag can be administered to all assigned study subjects for a total duration of 4 weeks (counted from the first day of eltrombopag administration) unless they meet one of the following criteria for removal from the study:

1. Withdrawal of consent. The patient's desire to withdraw from the study may occur at any time. The investigator should carefully consider whether the patient's withdrawal of consent is due to an adverse event, and if so, record the adverse event as the reason for withdrawal.
2. Violation of the study protocol, including a patient's failure to return for required treatments or assessments or failure on the part of participants with reproductive potential to practice effective birth control or non-compliance.
3. At the treating physician's clinical discretion, if any specific medical or psychosocial changes in patient's condition makes them unacceptable to further participate in the study.
4. If bone marrow biopsy performed to establish remission status (around day 30-45 of remission IC), confirm refractory or persistent disease or if there is leukemic involvement of extramedullary site (biopsy confirmation of skin or organ lesions, central nervous system involvement confirmed either by cerebrospinal fluid analysis or radiological exams) at any time during study.
5. Adverse events, including intolerance of eltrombopag not resolved by dose reduction, life threatening acute hypersensitivity reaction, persistent hepatotoxicity (refer to section 7.4.2), thrombosis/embolism (DVT, PE, stroke, TIA, myocardial infarction) other than central line thrombosis (refer to section 7.5.1) or evidence of disease progression on treatment (myeloid sarcomas). Participants who are removed from the study due to adverse events will be treated and followed according to established medical practice. All pertinent information concerning the outcome of such treatment will be entered in the CRF.

## 7.8 Duration of Follow Up

All study subjects who achieved a platelet count of 100,000/ $\mu$ L will be followed for a total up to 4 weeks from the stop date of eltrombopag or till the start date of post-remission therapy, whichever occurs earlier, for adverse events and response. The patients who are removed from study for unacceptable adverse events will be followed until that adverse event is resolved or stabilized. All patients will thereafter be followed for 5 years from study enrollment for relapse and survival endpoints as part of institutional standard of care policy for all treated AML patients.

## 8.0 CLINICAL MONITORING

### 8.1 Pre-induction Evaluation

Screening evaluation must be completed before starting remission IC and should include the following:

- 1) A signed informed consent.
- 2) Relevant medical history, including a detailed history for any antecedent hematologic disorder (AHD) and all treatments used for AHD including cytotoxic chemotherapy, radiation, or combined modality therapy. Review of all medications used during the 4-week period prior to screening date will be done.
- 3) CBC with differential at the time of diagnostic bone marrow biopsy for confirmation of AML. Documentation of all transfusions (red blood cells and platelets) along with dates of transfusion dating back to 8-weeks from the date of screening.
- 4) Physical examination and vital signs, including measurement of blood pressure, pulse, respiratory rate, pulse oximetry (oxygen saturation), height and body weight.
- 5) Assessment of ECOG performance status.
- 6) Documentation of AML classification according to the revised WHO 2008 classification.
- 7) Peripheral blood smear.
- 8) Bone marrow aspiration and biopsy for the following studies: cytologic analysis; morphologic assessment; flow cytometry assessment of marrow aspirate; CD34 immunostaining where necessary to enumerate marrow myeloblasts; metaphase cytogenetics; mutational analysis (especially c-kit mutations in favorable risk AML and NPM1, FLT3 and CEBPA mutations in patients with normal cytogenetics); and assessment of bone marrow fibrosis with reticulin and collagen staining. All these tests are currently done as routine standard of care. The results of mutational studies and metaphase cytogenetics are not necessary for starting patient on the study drug.
- 9) Comprehensive metabolic panel evaluations, including blood glucose, total protein, albumin, creatinine, blood urea nitrogen (BUN), serum bicarbonate ( $\text{CO}_2$ ), calcium, phosphorus, sodium, potassium, chloride, aspartate aminotransferase (AST), alanine aminotransferase (ALT), total bilirubin and alkaline phosphatase.
- 10) Remote hepatitis panel. ELISA for HIV.

- 11) A 12-lead electrocardiogram (ECG), following at least a 5-minute rest in supine position.
- 12) Baseline ophthalmological examination to be performed only in those presenting with new symptoms of visual impairment or insufficiency at the time of diagnosis of AML or those with known ocular conditions with accompanying vision defects.
- 13) Chest x-ray (2 views – PA and lateral), unless a previous x-ray taken during the 4 weeks prior to Day 1 of remission IC is available and shows no significant abnormality that would exclude the patient from the study.
- 14) Male participants with female partners of childbearing potential should have contraceptive measures addressed at screening, sufficient time to employ required contraceptive measures prior to Day 1 of IC, and confirmation of adequacy of contraceptive measures prior to receiving study drug.
- 15) Serum pregnancy test for women of childbearing status

## 8.2 Monitoring while taking eltrombopag

The following procedures will be conducted:

- 1) Daily vital signs and physical exam while inpatient and once weekly as outpatient only in those patients still receiving eltrombopag.
- 2) Adverse event (AE) monitoring and documentation will begin starting from the date of study drug initiation. Any AE resulting during or following remission IC but preceding study drug initiation will not be attributable to the study drug. AE's will be recorded as definite, probable, possible, unlikely or unrelated by the treating team in the daily clinical progress note and abstracted for study documentation by approved study personnel (physicians, research nurses and study coordinators).
- 3) CBC with differential will be monitored daily during hospital stay. Once the patient is discharged, CBC with differential will be checked within 72 hours, thereafter CBC with differential will be checked weekly until the subject's platelets reach 100,000/ $\mu$ L.
- 4) Complete metabolic panel (CMP) will be checked daily during hospital stay. Once the patient is discharged, CMP will be checked weekly until the subject's platelets reach 100,000/ $\mu$ L.
- 5) Documentation of all infections requiring treatment with intravenous antimicrobials (antibacterial, antiviral or antifungal) by date (the period to be covered for documentation purposes starts at day 1 of study drug administration).
- 6) Concurrent medication review (with each clinical assessment) for the entire period on the study drug.
- 7) Documentation of all red blood cell and platelet transfusions including dates of transfusion while on eltrombopag.
- 8) 12 lead electrocardiograms pre- and post-dose on the first day of eltrombopag administration and thereafter only if clinically indicated. The post-dose ECG is to be performed within a 2-4 hour window post-dose (preferably within 3 hours after administration of study medication). If assessment cannot be performed at 3 hours post-dose, record actual time of ECG performed.

- 9) All study subjects who achieve a platelet count of 100,000/ $\mu$ L will be followed for a total up to 4 weeks from the stop date of eltrombopag or till the start date of post-remission therapy, whichever occurs earlier, for adverse events and response. Adverse events that are related to the study drug (eltrombopag) will be followed through resolution or stabilization. CBCs and CMPs will be collected per standard of care as well as AEs for 4 weeks after stopping eltrombopag or till the start date of post-remission therapy, whichever occurs earlier.

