### **8.4 Long-term Follow-up**

All participants, regardless of reason for discontinuation, will be followed for survival and for AML transformation (an increase of blasts to a level  $\geq 20\%$  in peripheral blood or bone marrow) for five years from study registration as part of standard of care for CCF leukemia patients.

The following study calendar will be used:

	Pre- induction	Week 1	Week 2	Week 3	Week 4	Week 5	Week 6
						Inpatient/Outpatient	
Induction chemotherapy (IC)							
Study Medicationa							
Informed Consent	X						
Demographicsb	X						
Disease Characteristicsc	X						
Transfusion Historyd	X	X	X	X	X	X	X
Review of concurrent medications	X	X	X	X	X	X	X
Physical Examinatione	X	X	X	X	X	X	X
CSBEf	X	X	X	X	X	X	X
Performance statusg	X						
Hematologyh	X	X	X	X	X	X	X
Serum Biochemistryi	X	X	X	X	X	X	X
Chest x-ray	X						
Peripheral Blood Smearj	X					X	
Bone marrow biopsyk	X		D14 - 17			X	
Ophthalmology examl	X						
12 lead ECG	X			X m			
Adverse event monitoringn				X	X	X	X

Pre-induction assessment refers to evaluation at the time of diagnosis of AML prior to start of remission induction chemotherapy. Weeks as enumerated in the table refer to the time from the start date (day 1) of remission induction chemotherapy.

Week 1 is the week when the patient receives the standard 7+ 3 (cytarabine and anthracycline) remission induction chemotherapy

a. **Study Medication:** Eltrombopag dose as assigned. The drug will be started within 5 business days from the date of day 14 bone marrow biopsy if the day 14 bone marrow biopsy (range, 14-17) shows no morphological evidence of leukemia and will be continued for a total of 4 weeks unless discontinued earlier for reasons stated in the protocol.

b. **Demographics:** Date of birth, race, ethnicity, and gender.

c. **Disease Characteristics:** Date of AML diagnosis, AML category as classified by WHO, primary vs. secondary AML, type of secondary AML (antecedent hematologic disorder, therapy-related including prior radiation therapy and or cytotoxic chemotherapy for any condition).

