d. **Transfusion History:** Transfusion requirements of red blood cells and platelets up to 8 weeks prior to the diagnosis of AML and during hospital stay.

e. **Physical Examination:** Weight, height (during screening only), body temperature (oral), blood pressure, pulse rate, respiratory rate and pulse oximetry (oxygen saturation).

f. **CSBE:** Clinically Significant Bleeding Events includes hematuria, gastrointestinal bleed, retroperitoneal bleeding, intra-cranial bleed, epistaxis not controlled by conservative measures and muscle or soft tissue hematomas. CSBE will not include petechial skin rash, ecchymosis or mucosal petechiae.

g. **Performance Status** as per ECOG scale.

h. **Hematology:** CBC with differential will be monitored daily during hospital stay. Once the patient is discharged, CBC with differential will be checked within 72 hours, thereafter CBC with differential will be checked weekly until the subject's platelets reach 100,000/ $\mu$ L. Once the platelet counts reach 100,000/ $\mu$ L, the labs will be done at the discretion of treating physician as part of routine standard of care.

i. **Serum Biochemistry:** Complete metabolic panel (CMP) will be checked daily during hospital stay. CMP will include albumin, total protein, alkaline phosphatase, total bilirubin, SGOT[AST], SGPT[ALT], sodium, potassium, chloride, bicarbonate, BUN, creatinine, glucose, and calcium. Magnesium and phosphorus will be resulted if clinically indicated. Once the patient is discharged, CMP will be checked weekly until the subject's platelets reach 100,000/ $\mu$ L. Once the platelet counts reach 100,000/ $\mu$ L, the labs will be done at the discretion of treating physician as part of routine standard of care. ELISA for HIV and remote hepatitis panel will be checked only once at the time of study screening (pre-induction).

j. **Peripheral Blood Smear:** Will be performed prior to start of induction chemotherapy, typically between day 30 and 45 of induction chemotherapy while checking for remission status, and at the end of the study period (optional) based on clinical assessment.

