## 10.0 STUDY ENDPOINTS

### 10.1.1 Primary endpoint

The proportion of patients achieving a platelet count of  $\geq 50,000/\mu\text{L}$  by day 24 of IC on eltrombopag therapy. The treatment response parameters for platelet count recovery for this trial was derived from a cohort of 200 older AML patients (excluding acute promyelocytic leukemia and acute megakaryocytic leukemia) who underwent aggressive 7 + 3 cytarabine-based remission IC at the Cleveland Clinic between 2000 and 2011. The total CR rate in our historical cohort was 41%.

The median time to CR (defined as the time from the start date of IC to the achieving CR per

IWG criteria) was 34 days (range, 14-66). The median time to reach platelet counts  $> 50,000/\mu\text{L}$  was 24 days (range, 17-57) from the start date of IC.

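### No blood count is tied to induction day 24 for patients discharged before it, and the plan does not say how a patient without a day-24 count is scored on the primary endpoint

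*Combined protocol and SAP*

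**What the plan says.** Section 12.0 sets the endpoint: "The primary endpoint is the proportion of patients with early (by day 24 from the start of induction) platelet recovery" to at least 50,000/µL. Section 10.1.1 gives the same cut-off, "by day 24 of IC on eltrombopag therapy". Stage 1 uses it directly: "If eight or more (67%) have full platelet recovery by day 24 an additional 19 eligible patients will be assessed". The final rule accepts the drug if 21 or more of 31 patients recover.

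The blood count schedule is in section 8.2, item 3, and again in note h to the study calendar in section 8.4. In hospital, "CBC with differential will be monitored daily during hospital stay". Afterwards, "Once the patient is discharged, CBC with differential will be checked within 72 hours, thereafter CBC with differential will be checked weekly", until platelets reach 100,000/µL. Neither place mentions day 24, and no visit window refers to the primary endpoint.

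The plan has no rule for a patient whose status at day 24 was not observed. Section 12.0 sets its accrual goal in evaluable patients but does not define the term. Section 10.2 censors patients who do not recover, but only for the secondary time to platelet recovery. Section 7.6 replaces a patient who misses a dose through non-compliance; it does not address a missing count.

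**The concern.** The endpoint turns on one date, while the outpatient counts are timed from another. A patient who goes home below 50,000/µL, crosses the threshold shortly before day 24 and is next sampled after day 24 has recovered in time without any record of it.

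The cut-off lies where patients are crossing: section 10.1.1 reports a median of 24 days (range 17 to 57) to exceed 50,000/µL in the institution's historical cohort. A few unobserved days just before day 24 can therefore change a patient's status. The final decision can turn on a single patient, 20 against 21 of 31.

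Because scoring is not specified, the choice could be made after the data are seen. Counting such patients as non-recoveries lowers the observed rate. Dropping them as not evaluable pushes it the other way, since everyone dropped was below the threshold when last measured.

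**Working it through.** **1. Reproduce the stated design.** Inputs from section 12.0: 12 patients in stage 1, continue with 8 or more recoveries; 31 in total, accept with 21 or more; rates of 60% and 80%. With X1 ~ Bin(12, p) and X2 ~ Bin(19, p):

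- P(stop early) = P(X1 ≤ 7)
- P(accept) = Σ over x = 8 to 12 of P(X1 = x) · P(X2 ≥ 21 − x)
- P(reject) = 1 − P(accept)

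| True rate | Stop early (stated) | Reject overall (stated) |
|---|---|---|
| 60% | 56.2% (56%) | 80.6% (81%) |
| 80% | 7.3% (7%) | 8.9% (9%) |

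The stated figures reproduce to rounding.

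**2. Find the last scheduled count on or before day 24.** For discharge on day d, counts run daily to d, then fall on d + k, d + k + 7 and so on. Here k is 1, 2 or 3 days, because the first outpatient count may be taken at any time within 72 hours. The entries are days from the last count to day 24; 0 means a count falls on day 24.

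| Discharge day | 14 | 15 | 16 | 17 | 18 | 19 | 20 | 21 | 22 | 23 |
|---|---|---|---|---|---|---|---|---|---|---|
| k = 1 | 2 | 1 | 0 | 6 | 5 | 4 | 3 | 2 | 1 | 0 |
| k = 2 | 1 | 0 | 6 | 5 | 4 | 3 | 2 | 1 | 0 | 1 |
| k = 3 | 0 | 6 | 5 | 4 | 3 | 2 | 1 | 0 | 2 | 1 |

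For each k, 8 of the 10 discharge days leave day 24 without a count, and the longest gap is 6 days. In all uncovered cases the next count falls on days 25 to 30. These are calendar days, not patients. Under section 4.1, drug starts 7 to 9 days after the last day of induction, so discharge on days 14 to 16 may precede or coincide with drug start. Restricting to days 17 to 23 leaves 6 of 7 uncovered for each k.

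**3. Sensitivity of the decision rule.** Suppose the true rate is 80%, m percentage points of true recoveries go unobserved, and those patients are counted as non-recoveries. The rule then acts on p = 0.80 − m/100. The documents give no discharge distribution, so m is an assumed range.

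| m (points) | Observed rate | Share of recoverers missed | Expected patients of 31 | P(reject) |
|---|---|---|---|---|
| 0 | 80% | 0% | 0 | 8.9% |
| 2 | 78% | 2/80 = 2.5% | 0.02 × 31 = 0.6 | 13.2% |
| 4 | 76% | 4/80 = 5% | 0.04 × 31 = 1.2 | 18.7% |
| 8 | 72% | 8/80 = 10% | 0.08 × 31 = 2.5 | 33.0% |

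**4. Direction under the null.** Applying the same 5% and 10% missed shares to a true 60% gives observed rates of 0.60 × 0.95 = 57% and 0.60 × 0.90 = 54%. False acceptance falls from 19.4% to 11.8% and 6.6%.

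**The case against.** The strongest reply is that few patients may be affected. The endpoint is recovery by day 24, so any earlier qualifying count settles it. The calendar label "Inpatient/Outpatient" appears to sit at Week 5, whereas day 24 is in Week 4, which suggests that many patients were expected to be in hospital with daily counts at the cut-off. This largely stands. The table's layout is uncertain in the available text, though, and nothing in section 8.2 or note h rules out earlier discharge. A reader might infer that the endpoint cannot be read on its own date; that goes too far.

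A reader might also infer that unobserved recoveries are scored as failures. The documents contain no such rule; exclusion or replacement is equally open. The power figures hold only under the failure reading.

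It can be said that a site could time its draws to reach day 24. With the first draw 1 to 3 days after discharge, that is possible for discharge on days 14 to 16 and 21 to 23. But the plan permits this without requiring it, and for days 17 to 20 none of those timings reaches day 24.

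Finally, the reference rate may have the same gaps. Section 12.0 bases the statement that "approximately 60% of patients can be expected to recover platelets to" 50,000/µL by day 24 on historical and unpublished institutional data, and how often those patients were sampled is not stated. If they were sampled as sparsely after discharge, the 60% already reflects some missed recoveries, and closing the gap in the trial alone could slightly favour the drug. This stands as a caveat on the fix.

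**Conclusion.** The point holds in a limited form. The schedule as written can leave an early-discharged patient who has not yet reached 50,000/µL unobserved for up to 6 days before the cut-off, and the plan neither scores that patient nor defines evaluable.

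The size is unknown. The 8-of-10 figure describes discharge days and should not be read as a share of patients. The rise in rejection probability from 8.9% to between 13.2% and 33.0% rests on two assumptions: that 2 to 8 points of recoveries are missed, and that they are counted as non-recoveries. It shows sensitivity and is not a forecast. On those assumptions the loss is of power alone; a reader who infers an inflated risk of accepting an inactive drug has the direction wrong.

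This is a modest weakness in ascertaining the primary endpoint. It is worth correcting because the correction is cheap, and it does not invalidate the design.

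**What to change.** In section 8.2, item 3, and calendar note h: for every discharged patient without an earlier count of at least 50,000/µL, take one of the already scheduled outpatient blood counts on induction day 24, with later weekly draws running from that date.

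In section 12.0: define evaluable, state that treated patients with no qualifying count by day 24 stay in the denominator as not recovered, and report how many lacked a day-24 count. That scoring rule is conservative, and with the draw in place it should apply to few patients.

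The report should note that the sampling frequency behind the 60% reference is not stated, so ascertainment may differ slightly between the trial and its benchmark.

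The cost is a few sentences in three places and the re-timing of an existing draw. It adds no procedure and no patients, and treatment is unchanged.
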